9.3.4.2.4. Biochemical

Absolute and percent change from the month 0 visit to the final study visit in glycosaminoglycans (GAG), will be calculated for each subject, and summarized by presenting means, standard deviations, and 95% confidence intervals.

10. Confidentiality

Local transport of the Case Report Forms, source documents and specimens will be limited to the site's authorized staff. Study participants and/or respective guardians will be informed that information that identifies them or their child will be used only for the purpose of the study; this includes information that can help study personnel locate or contact them as well as information related to their or their child's medical condition (medical records, for example).

Data and specimens will be stored locally for at least 11 years as previously described. While the study is active, access to the stored data and specimens will be limited to approved study staff. After the study is closed, local access will be limited to the site's PI(s).

11. Certificate of Confidentiality

To help protect participant privacy, a Letter of Confidentiality has been obtained from the National Institutes of Health (NIH). With this Certificate, the researchers cannot be forced to disclose information that may identify a study participant, even by a court subpoena, in any federal, state, or local civil, criminal, administrative, legislative, or other proceedings. The researchers will use the Certificate to resist any demands for information that would identify a participant, except as explained below.

The Certificate cannot be used to resist a demand for information from personnel of the United States Government that is used for auditing or evaluation of Federally funded projects or for information that must be disclosed in order to meet the requirements of the federal Food and Drug Administration (FDA).

Even with the Certificate of Confidentiality, the investigators continue to have ethical obligations to report child abuse or neglect and to prevent an individual from carrying out any threats to do serious harm to themselves or others. If keeping information private would immediately put the study participant or someone else in danger, the investigators would release information to protect the participant or another person.

Department of Health and Human Services (DHHS) personnel may request identifying information for purposes of performing audits, carrying out investigations of DHHS grant recipients, or evaluating DHHS funded research projects.

12. Provisions to Monitor the Data to Ensure the Safety of subjects

12.1. Adverse Events

Subjects in this study will be closely monitored during the enzyme administration and for one hour afterward with frequent (every 15 minutes) vital signs and continuous pulse oximetry. The subject will be able to contact the investigator or other appropriate personnel to report adverse events occurring later. These will be treated with appropriate medical care where applicable. Adverse events that are unanticipated will be reported within 10 working days to the institutional review board.

An adverse event (AE) is any undesirable physical, psychological or behavioral effect (an unfavorable and unintended sign, symptom or disease) experienced by a subject during their participation in an investigational study whether or not product-related. This includes any untoward signs or symptoms experienced by the subject from the time of signing of the informed consent until completion of the study. Adverse events may include, but are not limited to:

- Subjective or objective symptoms spontaneously offered by the patient or subject and/or observed by the investigator or medical staff.
- Laboratory abnormalities of clinical significance.
- Disease signs, symptoms and/or laboratory abnormalities already existing prior to the use of the study medication are not considered adverse events after treatment unless they reoccur after the subject has recovered from the pre-existing condition or they represent an exacerbation in intensity or frequency.

All reportable AEs will be assigned a relationship to the study drug by the principal investigator. A drug-related AE is an event with a plausible time relationship to drug intake that cannot be explained by the disease or other drugs.

Any AEs experienced by the subject, from the time of signing the Informed Consent Form through the completion of study participation, will be reported as described (see Section 11.3) and recorded on the CRF. If AEs are present when the patient completes study participation, the subject will be re-evaluated within two weeks of completion and the results of this re-evaluation will be recorded on the CRF. If AEs are not resolved, additional follow-up will be performed as appropriate. All reportable AEs must be reported to the RDCRN within **20 working days** of the notification of the event or of the site becoming aware of the event.

Local institutional reporting requirements to IRBs, any CTSA oversight committee and the FDA, if appropriate, remain the responsibility of the site investigator and the Principal Investigator.

An unanticipated adverse event is defined as any adverse event, the specificity or severity of which is not consistent with the risks of information described in the protocol, and the event is related or possibly related to participation in the research, and suggests that the research places subjects or others at a greater risk or harm (including physical, psychological, economic, or social harm) than was previously known or recognized. Expected adverse events are those that are known to be associated with or have the potential to arise as a consequence of participation in the study.

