6.4. Study Timelines

The duration of each subject's participation in the study is expected to be five years. We anticipate enrolling these subjects over a 4-year period. The estimated date of completion of the study is 10 years following the onset of the study.

7. Procedures Involved in the Human Research

This study is a five-year open-label, prospective trial in 6 MPS I subjects age six years or greater who have completed a 24-month open label study (MIRC-002). Potentially eligible subjects who (or, if appropriate whose parents or guardians) have provided signed, written informed consent will first participate in a baseline screening phase. This will occur at least six months after subjects have completed the MIRC002 pilot study. During baseline screening, the subjects will receive the baseline evaluations outlined below, and their eligibility will be determined. Every three months, subjects will receive intrathecal recombinant human α-L-iduronidase (IT rhIDU) approved as Aldurazyme® [laronidase] for the treatment of cognitive impairment in patients with mucopolysaccharidosis I (MPS I). Neuropsychological testing and MRI will be performed at baseline and at one year intervals. Safety will be monitored continuously throughout the subject's study participation through recording all adverse events (AEs) and periodically performing clinical and laboratory evaluations.

Study subjects will receive intrathecal enzyme therapy only during the study; intrathecal enzyme therapy will not be administered at the end of the five-year period. If further intrathecal enzyme is desired, the subject may enroll in further intrathecal research if another study is available.

To assure that subjects enrolling in the trial have maximum access to alternative therapy, subjects will be asked to receive counseling regarding other available appropriate medical and surgical alternatives prior to enrollment in this trial.

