The diluted enzyme will be administered via lumbar puncture and given slowly over 2-3 minutes. The subject will be watched closely during enzyme administration for any adverse clinical reactions. After enzyme administration, the subject will lie supine in Trendelenberg (head below the level of the legs) for a period of one hour with monitoring continued. If the subject is unable to tolerate the Trendelenberg position, he or she may lie down in a position of comfort. The subject should be observed for another 3 hours supine or lying down in an alternative position of comfort. Subjects will remain hospitalized for a minimum of 24 hours from the time of the intrathecal injection. During hospitalization, vital signs, including pulse, respiration, blood pressure, pulse oximetry, and temperature will be checked every 4 hours. Neuro checks, including assessment of level of consciousness, sensation and movement, will be done q15 minutes during the first hour post-procedure, then hourly for the next 3 hours, and q4 hours thereafter during the 24 hour inpatient monitoring period. Discharge may not occur if any headache or pain greater than baseline for the subject are present. New narcotic analgesics may not be administered on an outpatient basis to study subjects. Family members will be provided clear instructions regarding the post discharge monitoring of the subject for anticipated adverse events. The day following discharge from the inpatient unit, the subject will return for an outpatient visit. A physical and neurologic examination and interim history will be performed. Re-hospitalization will occur if new neurologic symptoms, signs, or pain (greater than the subject's baseline) are present at this follow up visit. The above procedure will be followed for all subjects for all treatment visits.

Radiologically-guided lumbar puncture may be required in certain individuals due to body habitus or other factors. This will be performed under fluoroscopy or ultrasound guidance at the discretion of the investigator.

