7.8.1.2.2. Complete blood count and chemistries

Blood for a complete blood count and serum chemistries (including basic chemistries, liver function tests, renal function tests) will be performed according to the schedule above. Analyses will be performed at a local clinical laboratory. Age-appropriate normal values for the laboratory will be used for comparison.

The investigator must score all abnormal laboratory values as either clinically significant (CS) or not clinically significant (NCS). Some laboratory values may be outside of the normal value range because of the underlying disease. As in routine practice the investigator should use clinical judgment when considering clinical significance. Clinical significant worsening is defined as any variation in laboratory parameters that has medical relevance and results in an alteration in medical care.

If clinically significant laboratory worsening from baseline is noted, the changes will be documented on the appropriate adverse event form and will be followed as an adverse event consistent with the procedure outlined in Sections 11.1,

11.2, and 11.3. The investigator will also assess the relationship of all clinically significant abnormal values to program drug as being none, remote, possible, probable, or definite.

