12.8. RDCRN Adverse Event Data Management System (AEDMS)

Upon entry of a serious adverse event by a site investigator, the DMCC created Adverse Event Data Management System (AEDMS) will immediately notify the Principal Investigator. The Principal Investigator is responsible for notifying NINDS staff.

Serious adverse events: The site investigator determines causality (definitely not related, probably not related, possibly related, probably related, definitely related) of the adverse event. The DSMB will also review the SAE incident report.

The DSMB may request further information if necessary and possibly suggest changes to the protocol or consent form to the NINDS as a consequence of adverse events. A back-up notification system is in place so that any delays in review by the DSMB chair beyond a specified period of time are forwarded to a secondary reviewer. The Adverse Event Data Management System (AEDAMS) maintains audit trails and stores data (and data updated) and communication related to any adverse event in the study.

Non-serious expected adverse events Except those listed above as immediately reportable, non-serious expected adverse events that are reported to or observed by the investigator or a member of his/her research team will be

submitted to the DMCC in a timely fashion (within 20 working days). The events will be presented in tabular form and given to the DSMB on a quarterly basis or as requested. Local site investigators are also required to fulfill all reporting requirements of their local institutions.

The DMCC will post aggregate reports of all adverse events (serious/not serious and expected, unexpected) for site investigators and IRBs.

All reported adverse events will be classified using the current version of the Common Terminology Criteria for Adverse Events (CTCAE) developed and maintained by CTEP at National Cancer Institute.

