12.10. Discontinuation Guidelines

The participation of all study subjects will be halted pending review by the NIH, DSMB and IRB for the following reasons:

- WHO Grade 3 toxicity (such as a seizure or meningitis) is experienced by 2 or more subjects
- Death or WHO Grade 4 toxicity is experienced by 1 or more subjects

If one of the above conditions are met, the study will be placed on hold (no new enrollment, and a halt to all study procedures on enrolled subjects), and the PI will notify the NIH, IRB and DSMB within 24 hours.

This study may be also suspended or closed if:

- Accrual has been met
- The study objectives have been met
- The Study Chair / Study Investigators believe it is not safe for the study to continue
- The RDCRN DSMB suspends or closes the trial
- The NIH suspends or closes the trial
- The FDA suspends or closes the trial

13. Data Quality Assurance

All required data will be recorded on the CRF. All missing data will be explained. If a space is blank because the item was not done, the item will be marked "ND." If the item is unknown, item will be marked "UNK." If the item is not applicable to the individual case, the space will be marked with a "NA." If the item is not available, it will be marked with "NAV." All entries will be recorded in black ink. If an entry error has been made, a single straight line will be drawn through the wrong entry and the correct data will be entered above it and initialed and dated. ERRORS MAY NOT BE ERASED AND WHITEOUT MAY NOT BE USED.

The CRFs will be reviewed manually at the study site for completeness. All data will be entered into a study database for analysis and reporting. Any data captured electronically (e.g., laboratory data) will be electronically transferred to the database. Upon completion of data entry, the database will receive a quality assurance (QA) check to ensure acceptable accuracy and completeness.

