15.5. Risks from study procedures

Spinal tap: Subjects may experience some discomfort from the spinal tap. This may include back pain, headache, lightheadedness and feeling faint. It is also possible and rare that a spinal headache may develop. More serious and rare

side effects from a spinal tap include paralysis, nerve injury, spinal hematoma, spinal herniation, and death.

Sedation medicine given for the spinal tap may cause sleepiness, nausea, vomiting, blurry vision, light-headedness, chills, yawning, loss of balance, nervousness, confusion, hallucinations, anxiety, restlessness, sleep problems, nightmares, and feeling happy or unhappy. Subjects may also experience stomach discomfort, an acid taste, coughing, hiccoughs, excessive drooling, and/or throwing up. The chance of these side effects occurring is low, and they are usually temporary and not serious. Rarely, some people who receive the medicine have slurred speech, tingling or other sensation, rapid eye movements, and other movements including convulsion-type movements.

More serious side effects can occur from the sedation medication; these include difficulty breathing, not breathing, heart beating too slow or too fast, or an allergic reaction.

The numbing cream and the other medicine given to numb the subject's back may also cause side effects. These include shivering, nausea, numbness, light-headedness, nervousness, feeling scared, confusion, dizziness, drowsiness, ringing in the ears, blurred vision, seeing double, feeling hot or cold, twitching, shaking, convulsions, fainting, and feeling happy. The chance of these side effects occurring is low, and they are usually temporary and not serious. Some people who receive the medicines have pain, redness, or swelling on the spot on their body where the medicine is injected. These are also usually temporary and not serious.

More serious side effects can occur, including loss of consciousness, breathing too slow, not breathing, irregular heartbeat, and death. The chance of these serious side effects occurring is very low, and the study doctor and her staff will take every precaution to prevent them or treat them immediately.

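### The definition of a drug-related adverse event has no term for the lumbar puncture and excludes whatever MPS I could explain, so attribution of non-serious clinical events can be wrong in either direction

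*Combined protocol and SAP*

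**What the plan says.** **Definition and record.** Section 12.1 says "All reportable AEs will be assigned a relationship to the study drug by the principal investigator", and then "A drug-related AE is an event with a plausible time relationship to drug intake that cannot be explained by the disease or other drugs". Section 12.3 lists what the CRF must hold for each AE and SAE; its only causality item is relationship to study drug.

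**Delivery.** Section 7.6: "The diluted enzyme will be administered via lumbar puncture and given slowly over 2-3 minutes". The opening of Section 7 sets the frequency ("Every three months, subjects will receive intrathecal recombinant human" α-L-iduronidase) over a five-year study. Section 15.5 says of the spinal tap itself: "This may include back pain, headache, lightheadedness and feeling faint".

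**Other causality scales.** Section 7.8.1.2.2 has the investigator rate clinically significant abnormal laboratory values against the drug "as being none, remote, possible, probable, or definite". Section 12.8 has the site investigator rate serious adverse events as "definitely not related, probably not related, possibly related, probably related, definitely related", without saying related to what.

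**Where procedures do count.** Section 12.9 names study procedures as a possible cause, and the unanticipated-event definition in 12.1 refers to participation in the research. Both apply only to unanticipated events or problems.

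**Where attribution is used.** Section 12.7 requires periodic reports listing adverse events with severity and attribution. The tables in 9.3.3.2 to 9.3.3.4 count subjects with events and do not split by relatedness. Section 12.10 halts the study on criteria such as "WHO Grade 3 toxicity (such as a seizure or meningitis) is experienced by 2 or more subjects", with no stated condition on relatedness.

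**The concern.** Long-term safety of intrathecal rhIDU is the first objective in Section 1. The trial is open-label, has no concurrent control arm and enrols at most six subjects. Drug and puncture always start together, so no comparison of groups can separate them. What remains is the judgement made on each event when it occurs, and the definition constrains that judgement badly. It has no way to say that the puncture caused an event, and it removes an event from the drug's account whenever the disease is a possible explanation. At stake is whether a statement about drug-related events from this trial can be taken at face value, and whether the reports required by 12.7 show useful attribution to those monitoring safety.

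**Working it through.** The documents attach no figure to this definition, so there is nothing to reproduce. The check is to apply the rule as a logical test and then show the scale.

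**1. The rule as a test.** Drug-related = (timing plausible) AND (disease cannot explain it) AND (other drugs cannot explain it).

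| Event | Timing plausible | Disease could explain | Other drug could explain | Label under 12.1 |
|---|---|---|---|---|
| New back pain from the puncture | yes | no | no | drug-related |
| Puncture headache, subject without headache or hydrocephalus from MPS I | yes | no | no | drug-related |
| Puncture headache, subject with headache or hydrocephalus from MPS I | yes | yes | no | not drug-related |
| True rhIDU effect that looks like MPS I (headache, hydrocephalus) | yes | yes | no | not drug-related |
| Nausea from sedation | yes | no | yes | not drug-related |

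The disease column rests on the protocol. Section 2 says most MPS I patients develop hydrocephalus and that it can cause chronic headache. Section 7.7.3.5 lists headache among the symptoms checked at baseline. Rows 1 and 2 charge a delivery effect to the drug. Row 4 removes a drug effect from the drug. Rows 2 and 3 give the same event opposite labels, depending on the subject's disease history.

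**2. Do the other scales repair this?** The scale in 7.8.1.2.2 covers laboratory values only. The scale in 12.8 covers serious events and names no object. For a non-serious clinical event, 12.1 is the only stated definition. The regimes also overlap: a clinically significant laboratory worsening is recorded as an adverse event, and if serious it falls under 12.8 as well. Three rules would then apply to one event, with no statement of which governs.

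**3. Exposure.**
- Doses per subject: 60 months / 3 months = 20. Table 1 in 7.2 shows no rhIDU at the End Study visit, which agrees with 20 rather than 21.
- Dosing punctures: 6 x 20 = 120. Section 4 anticipates 67% enrolment, about 4 of 6 subjects: 4 x 20 = 80.
- Punctures without rhIDU: one baseline CSF flow study per subject (7.7.5.1), so at most 6.

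**4. Illustration only.** The documents give no rate of puncture effects. Let p be an assumed rate per puncture, with punctures independent and all 20 doses given. The chance that a subject has at least one puncture effect is 1 - (1 - p)^20.

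| Assumed p | Chance per subject | Expected subjects of 6 | Expected events in 120 punctures |
|---|---|---|---|
| 2% | 33% | 2.0 | 2.4 |
| 5% | 64% | 3.9 | 6 |
| 10% | 88% | 5.3 | 12 |
| 30% | 99.9% | 6.0 | 36 |

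With 4 subjects and p = 5%, expected events are 0.05 x 80 = 4. These figures count puncture effects, not mislabelled ones. Any the disease could explain would be labelled not drug-related, and the documents give no basis for that split.

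**The case against.** The strongest reply is that little in the plan depends on the label.

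- **Safety tables and halting rule.** A reader might infer that the definition biases the planned event rates or decides when the study halts. The documents do not support that. The 9.3.3 tables count events whatever their cause, 12.1 still counts worsening of existing disease signs as an adverse event, and 12.7 keeps disease-related events in the reports to the DSMB. Section 12.10 works on grade or death; the word toxicity alone does not make relatedness a condition. This part of the reply stands in full.
- **Seizure.** It is tempting to add seizure as a toxicity that the disease clause would hide. No section lists seizure as a manifestation of MPS I, 15.2 attributes the canine seizures to the formulation buffer, and 12.10 names seizure as a toxicity. The example fails.
- **All puncture effects counted against the drug.** This is also too strong. Headache is a disease symptom too, sedation effects fall under other drugs, and 15.5 calls spinal headache rare.
- **Graded scales exist.** Serious events and abnormal laboratory values can be rated as possibly related, so disease-like toxicity in those classes need not be lost. True, but non-serious clinical events are left out, and neither scale separates drug from puncture.
- **Unseen material.** The CRF, the Study Operations Manual, the DSMB charter and the reporting flowchart are not available, and any of them might carry a procedure field. This limits the claim to what the protocol text requires.
- **Limits of the remedy.** A second field records an opinion and cannot truly separate two causes with the same starting time. Counting delivery effects against an intrathecal product is arguably conservative. The first point stands. The second covers only one direction of error: excluding drug effects that resemble the disease is not conservative.

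**Conclusion.** The concern holds in a limited form. For non-serious clinical events, the definition in 12.1, applied as written, can attribute puncture effects to rhIDU and excludes rhIDU effects that MPS I could explain. It is also not reconciled with the scales in 7.8.1.2.2 and 12.8. The harm is confined to the attribution reported under 12.7 and to any later claim about drug-related events. All-cause capture, the 9.3.3 tables and the halting rule as written are unaffected.

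The number of mislabelled events cannot be derived. A range of about 4 to 36 puncture effects over the study follows only from an assumed 5% to 30% rate per puncture with 4 to 6 subjects, and not all of these would be mislabelled. The conclusion itself needs no rate. It rests on the wording of 12.1 and 12.3, on delivery by lumbar puncture at every dose, and on the assumption that no unseen form or manual already adds procedure attribution. It should be corrected because safety is the first objective, there is no concurrent control, and attribution not recorded when an event occurs is hard to reconstruct.

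**What to change.** 1. In 12.1, replace the yes/no definition with one graded causality scale for all adverse events; the five-level scale in 12.8 would serve.
2. Rate each event separately for (a) rhIDU and its diluent and (b) study procedures: lumbar puncture, sedation or anaesthesia, and the radionuclide flow study. Allow more than one cause.
3. Remove explicability by the disease as an automatic exclusion. The investigator can still weigh it in choosing the level.
4. Reconcile 7.8.1.2.2, 12.1, 12.3 and 12.8 and the CRF so that one scale applies, with its object named.
5. In 9.3.3, add a table of adverse events by attribution to (a) and (b) beside the all-cause table, which stays the main display.

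The cost is a wording change, an extra CRF field per event and one more table. Some events will be rated related to both drug and procedure, and the attribution remains investigator judgement, which the report should say.
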